6.3. Exploratory Efficacy Endpoints

6.3.1. Definition of Exploratory Efficacy Endpoints

PPD

[REDACTED]

6.4. Changes From Protocol-Specified Efficacy Analyses

Instead of comparing the SVR12 rate in all treated subjects (3 to < 18 years of age) against the historical SVR12 rate of 80% by using the 2-sided exact 1-sample binomial test at the 0.05 significance level as specified in the protocol, a sequential test method was used to firstly perform the above statistical test in the adolescent subjects (12 to < 18 years of age). Only if the superiority is demonstrated in adolescents, the SVR12 rate in the remaining subjects (3 to < 12 years of age) will be compared with 80% at the 0.05 significance level. The test in adolescents was described in a separate SAP for Adolescents SVR12 Analysis. Details of the test in this Final Analysis are described in Section [6.1.3](#).

7. SAFETY ANALYSES

7.1. Adverse Events and Deaths

7.1.1. Adverse Event Dictionary

Clinical and laboratory adverse events (AEs) will be coded using Medical Dictionary for Regulatory Activities (MedDRA). System organ class (SOC), high-level group term (HLGT), high-level term (HLT), preferred term (PT), and lower-level term (LLT) will be provided in the AE dataset.

7.1.2. Adverse Event Severity

Adverse events are graded by the investigator as Grade 1, 2, 3, or 4 according to toxicity criteria specified in the protocol. The severity grade of events for which the investigator did not record severity will be categorized as “missing” for tabular summaries and data listings and the most severe will be considered (for sorting purpose only) in data presentation.

7.1.3. Relationship of Adverse Events to Study Drug

Related AEs are those for which the investigator selected “Related” on the AE eCRF to the question of “Related to Study Treatment”. Events for which the investigator did not record relationships to study drug will be considered related to study drug for summary purposes. However, by-subject data listings will show the relationship as missing from that captured on the CRF.

7.1.4. Serious Adverse Events

Serious adverse events (SAEs) will be identified and captured as SAEs if AEs met the definitions of SAE specified in the study protocol. Serious adverse events captured and stored in the clinical database will be reconciled with the SAE database from the Gilead Pharmacovigilance and Epidemiology Department before database finalization.

7.1.5. Treatment-Emergent Adverse Events

7.1.5.1. Definition of Treatment Emergent

Treatment-emergent adverse events (TEAEs) are defined as one or both of the following:

- Any AEs with an onset date on or after the study drug start date and no later than 30 days after permanent discontinuation of study drug.
- Any AEs leading to premature discontinuation of study drug.

7.1.5.2. Incomplete Dates

If the onset date of the AE is incomplete, then the month and year (or year alone if month is not recorded) of onset determine whether an AE is treatment emergent, as long as the AE stop date is not prior to the first dose date of study drug. The event is considered treatment emergent if both of the following 2 criteria are met:

- The AE onset and end dates are the same as or after the month and year (or year) of the first dose date of study drug
- The AE onset date is the same as or before the month and year (or year) of the 30th day after the date of the last dose of study drug

An AE with completely missing onset and stop dates, or with the onset date missing and a stop date later than the first dose date of study drug, will be considered to be treatment emergent.

7.1.6. Summaries of Adverse Events and Deaths

A brief high-level summary of TEAEs will be provided by treatment group and by the number and percentage of subjects who had the following: any AE; any AE of Grade 3 or above; any AE of Grade 2 or above; any treatment-related AE; any treatment-related AE of Grade 3 or above; any treatment-related AE of Grade 2 or above; any SAE; any treatment-related SAE; any AE that led to premature discontinuation of any study drug; any AE that led to premature discontinuation of SOF; any AE that led to premature discontinuation of RBV; any AE that led to modification or interruption of any study drug; any AE that led to interruption of SOF; any AE that led to modification or interruption of RBV. All deaths (including those that are treatment emergent and those that are not treatment emergent) observed during the study will also be summarized and included in this table. Additional brief high-level summary of TEAEs will be provided by treatment group defined in [Table 3-2](#) for 3 to < 6 years of age subjects.

Adverse event summaries will provide the number and percentage of subjects with TEAEs by SOC and PT, by treatment group based on the Safety Analysis Set as follows:

- All AEs
- AEs of Grade 3 or above
- AEs of Grade 2 or above
- All treatment-related AEs
- Treatment-related AEs of Grade 3 or above
- Treatment-related AEs of Grade 2 or above
- All SAEs
- All treatment-related SAEs

- All AEs leading to premature discontinuation of study drug
- AEs leading to premature discontinuation of SOF
- AEs leading to premature discontinuation of RBV
- AEs leading to modification or interruption of any study drug
- AEs leading to interruption of SOF
- AEs leading to modification or interruption of RBV

Multiple events will be counted only once per subject in each summary. Adverse events will be summarized and listed first in alphabetic order of SOC and then by PT in order of descending incidence of the pooled treatment groups within each SOC. In summaries by severity grade, the most severe grade will be used for those AEs that occurred more than once in an individual subject during the study.

In addition to the above summary tables, TEAEs will be summarized by PT only, in order of descending incidence within the pooled treatment groups for:

- AEs that occurred in at least 5% of subjects within any treatment group
- AEs of Grade 3 or above
- All treatment-related AEs
- All SAEs
- AEs leading to premature discontinuation of study drug
- AEs leading to premature discontinuation of SOF
- AEs leading to premature discontinuation of RBV
- AEs leading to modification or interruption of any study drug
- AEs leading to interruption of SOF
- AEs leading to modification or interruption of RBV

In addition to the by-treatment summaries described above, data listings will be provided for the following:

- All AEs (with a variable indicating whether the event is treatment emergent)
- AEs of Grade 3 or above

- SAEs
- Deaths
- AEs leading to premature discontinuation of study drug
- AEs leading to modification or interruption of any study drug

7.2. Laboratory Evaluations

Laboratory data collected during the study will be analyzed and summarized using both quantitative and qualitative methods. Summaries of laboratory data will be provided for the Safety Analysis Set and will include data collected up to the last dose of study drug plus 30 days for subjects who have permanently discontinued study drug or all available data at the time of the database snapshot for subjects those who were ongoing at the time of an interim analysis. The analysis will be based on values reported in conventional units. When values are below the limit of quantitation, they will be listed as such, and the closest imputed value will be used for the purpose of calculating summary statistics. For example, if “< 0.2” was recorded, a value of 0.1 will be used for the purpose of calculating summary statistics; if “< 0.1” was recorded, a value of 0.09 will be used for the purpose of calculating summary statistics.

A by-subject listing for laboratory test results will be provided by subject ID number and visit in chronological order for hematology, serum chemistry, and urinalysis separately. Values falling outside of the relevant reference range and/or having a severity grade of 1 or higher on the Gilead Grading Scale for Severity of Adverse Events and Laboratory Abnormalities will be flagged in the data listings, as appropriate.

No inferential statistics will be generated.

7.2.1. Summaries of Numeric Laboratory Results

Descriptive statistics (n, mean, SD, median, Q1, Q3, minimum, and maximum) will be provided by treatment group for ALT, AST, total bilirubin, alkaline phosphatase, hemoglobin, reticulocytes, white blood cell (WBC), neutrophils, lymphocytes, platelets, and INR as follows:

- Baseline values
- Values at each postbaseline analysis window
- Change from baseline at each postbaseline analysis window

A baseline laboratory value will be defined as the final assessment performed on or prior to the date/time of first dose of study drug. Change from baseline to a postbaseline visit will be defined as the visit value minus the baseline value. The mean, median, Q1, Q3, minimum, and maximum will be displayed to the reported number of digits; SD to the reported number of digits plus 1.

Median (Q1, Q3) of the observed values for these laboratory parameters will be plotted using a line plot by treatment group and visit.

In the case of multiple values in an analysis window, data will be selected for analysis as described in Section 3.7.3 (Selection of Data in the Event of Multiple Records in a Window).

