#### **1.5. Rationale for Dose Selection of SOF**

SOF 400 mg, once daily, when dosed in combination with RBV with or without PEG has demonstrated broad genotypic efficacy and favorable safety profile in over 3300 HCV-infected adult subjects across multiple patient populations in Phase 2 and 3 trials. This dose is the marketed dose of SOF for the treatment of HCV-infection in adults.

[figure not shown]
Selection of doses of SOF for adolescents and younger age groups will target systemic exposures similar to those observed in adults at the marketed dose. SOF is a substrate for efflux drug transporters P-glycoprotein (P-gp) and breast cancer resistance protein (BCRP). SOF is extensively metabolized to the pharmacologically active nucleoside analog phosphate. The

activation pathway involves hydrolysis by intestinal and hepatically expressed carboxylesterase (CES1) and Cathepsin A (CatA) enzymes {20287}, {20288}. SOF is also converted to GS-331007, an inactive circulating metabolite, which is eliminated renally by active tubular secretion and glomerular filtration. Available data suggest comparable hepatic expression of CES1 in adolescents and adults with modestly decreased expression in children. However, little is known about the developmental regulation of Pgp, CES, and CatA. When adjusted for BSA, the processes of active secretion and glomerular filtration approximate adult activity by 6 to 12 months of age {5914}.

The adult clinical dose of SOF 400 mg or a lower dose, SOF 200 mg are being evaluated in adolescent subjects (12 to <18 years old, weighing  $\geq$  45 kg) or pediatric subjects (6 to < 12 years old, weighing  $\geq$  17kg and < 45kg), respectively. The appropriateness of these doses is supported by data from the PK Lead-ins which demonstrated comparable SOF and GS-331007 exposures in adolescent subjects who received sofosbuvir 400 mg or pediatric subjects (6 to < 12 years old) who received sofosbuvir 200 mg and in adult subjects in Phase 2/3 using population PK analyses.

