### 4.3. Exclusion Criteria

Subjects who meet *any* of the following exclusion criteria are not to be enrolled in this study.

1. Pregnant or lactating subjects
2. Sexually-active males or females of childbearing potential who are not willing to use an effective method of contraception during the study (see [Appendix 5](#) for further details)
3. Decompensated liver disease defined as INR  $> 1.2 \times$  ULN, platelets  $< 50,000/\text{mm}^3$ , serum albumin  $< 3.5$  g/dL, or prior history of clinical hepatic decompensation (e.g., ascites, jaundice, encephalopathy, variceal hemorrhage)
4. Chronic liver disease of a non-HCV etiology (e.g., hemochromatosis, Wilson's disease, alpha-1 antitrypsin deficiency)
5.  $\alpha$ -fetoprotein  $> 50$  ng/mL
6. Serum creatinine  $> 1.5$  mg/dL
7. Estimated glomerular filtration rate  $< 90$  mL/min/ $1.73\text{m}^2$ , as calculated by the Schwartz Formula
8. Evidence of hepatocellular carcinoma (HCC) or other malignancy (with the exception of certain resolved skin cancers)
9. Co-infection with HIV, acute HAV, or HBV
10. Significant cardiovascular, pulmonary or neurological disease
11. Evidence of a gastrointestinal malabsorption syndrome that may interfere with absorption of orally administered medications
12. History of solid organ or bone marrow transplantation
13. Chronic daily non-steroidal anti-inflammatory drug therapy
14. Systemic corticosteroid use for  $\geq 5$  days (pulmonary/nasal administration is permitted)
15. Investigational agents taken within the past 28 days (except with the expressed approval of the Sponsor)
16. Clinically-relevant alcohol or drug abuse within 12 months of screening. A positive drug screen will exclude subjects unless it can be explained by a prescribed medication; the diagnosis and prescription must be approved by the investigator
17. Known hypersensitivity to the study drugs, the metabolites or formulation excipients
18. Any other condition (including alcohol or substance abuse) or prior therapy that, in the opinion of the Investigator, would make the subject unsuitable for the study or unable to comply with dosing requirements
19. Use of any prohibited concomitant medications as described in [Section 5.6](#) within 28 days of the Day 1 visit

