#### **6.6.10. Estimated Glomerular Filtration Rate (GFR)**

Estimated Glomerular Filtration Rate (GFR) using Schwartz Formula ( $\text{mL}/\text{min}/1.73\text{m}^2$ )  
 $= k \times L/\text{Scr}$  [(k is a proportionality constant, for adolescent females  $\geq 12$  years old is 0.55; for adolescent males  $\geq 12$  years old is 0.70, and for children 3- <12 years old is 0.55); L is height in centimeters (cm); and  $S_{\text{cr}}$  is serum creatinine (mg/dL)]

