Hypouricemia Adult and Pediatric ≥ 1 year	1.5 mg/dL to < LLN 87 µmol/L to < LLN	1.0 to < 1.5 mg/dL 57 to < 87 µmol/L	0.5 to < 1.0 mg/dL 27 to < 57 µmol/L	< 0.5 mg/dL < 27 µmol/L
Infant < 1 Year	N/A	1.0 mg/dl to <LLN- 57 µmol to <LLN	0.5 to < 1.0 mg/dL 27 to < 57 µmol/L	< 0.5 mg/dL < 27 µmol/L
Creatinine**	> 1.50 to 2.00 mg/dL > 133 to 177 µmol/L	> 2.00 to 3.00 mg/dL > 177 to 265 µmol/L	> 3.00 to 6.00 mg/dL > 265 to 530 µmol/L	> 6.00 mg/dL > 530 µmol/L
Bicarbonate Adult and Pediatric ≥ 4 Years	16.0 mEq/L to < LLN 16.0 mmol/L to < LLN	11.0 to < 16.0 mEq/L 11.0 to < 16.0 mmol/L	8.0 to < 11.0 mEq/L 8.0 to < 11.0 mmol/L	< 8.0 mEq/L < 8.0 mmol/L
Pediatric < 4 Years	NA	11.0 mEq/L to <LLN 11.0 mmol/L to <LLN	8.0 to < 11.0 mEq/L 8.0 to < 11.0 mmol/L	< 8.0 mEq/L < 8.0 mmol/L
Triglycerides (Fasting)	NA	500 to 750 mg/dL 5.64–8.47 mmol/L	> 750 to 1200 mg/dL > 8.47–13.55 mmol/L	> 1200 mg/dL > 13.55 mmol/L

CHEMISTRY				
	Grade 1	Grade 2	Grade 3	Grade 4
LDL (Fasting) Adult	130 to 160 mg/dL 3.35 to 4.15 mmol/L	>160 to 190 mg/dL >4.15 to 4.92 mmol/L	> 190 mg/dL >4.92 mmol/L	NA
LDL (Fasting) Pediatric >2 to <18 years	110 to 130 mg/dL 2.84 to 3.37 mmol/L	>130 to 190 mg/dL >3.37 to 4.92 mmol/L	> 190 mg/dL >4.92 mmol/L	NA
Hypercholesterolemia (Fasting)	200 to 239 mg/dL 5.16 to 6.19 mmol/L	> 239 to 300 mg/dL > 6.19 to 7.77 mmol/L	> 300 mg/dL > 7.77 mmol/L	NA
Pediatric < 18 Years	170 to 199 mg/dL 4.39 to 5.15 mmol/L	> 199 to 300 mg/dL > 5.15 to 7.77 mmol/L	> 300 mg/dL > 7.77 mmol/L	NA
Creatine Kinase	3.0 to < 6.0 × ULN	6.0 to < 10.0 × ULN	10.0 to < 20.0 × ULN	≥ 20.0 × ULN

\*Calcium should be corrected for albumin if albumin is < 4.0 g/dL

\*\* An overlap between the Grade 1 scale and the Lab's normal range for creatinine may result for Male subjects >70 yrs. Please follow the Gilead convention of grading any result within the LLN and ULN a 0.

ENZYMES				
	Grade 1	Grade 2	Grade 3	Grade 4
AST (SGOT)	1.25 to 2.50 × ULN	> 2.50 to 5.00 × ULN	> 5.00 to 10.00 × ULN	> 10.00 × ULN
ALT (SGPT)	1.25 to 2.50 × ULN	> 2.50 to 5.00 × ULN	> 5.00 to 10.00 × ULN	> 10.00 × ULN
GGT	1.25 to 2.50 × ULN	> 2.50 to 5.00 × ULN	> 5.00 to 10.00 × ULN	> 10.00 × ULN
Alkaline Phosphatase	1.25 to 2.50 × ULN	> 2.50 to 5.00 × ULN	> 5.00 to 10.00 × ULN	> 10.00 × ULN
Total Amylase	> 1.0 to 1.5 × ULN	> 1.5 to 2.0 × ULN	> 2.0 to 5.0 × ULN	> 5.0 × ULN
Pancreatic Amylase	> 1.0 to 1.5 × ULN	> 1.5 to 2.0 × ULN	> 2.0 to 5.0 × ULN	> 5.0 × ULN

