7.2.2. Graded Laboratory Values

The Gilead Grading Scale for Severity of Adverse Events and Laboratory Abnormalities will be used for assigning toxicity grades to laboratory results for analysis as Grade 0, Grade 1, Grade 2, Grade 3, or Grade 4. Grade 0 includes all values that do not meet the criteria for an abnormality of at least Grade 1. Some laboratory tests have criteria for both increased and decreased levels; analyses for each direction (i.e. increased, decreased) will be presented separately.

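### The only planned summary of on-treatment creatinine is a graded table that starts above 1.50 mg/dL, a cut-off too high to show most renal decline in younger children

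*SAP*

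**What the plan says.** Creatinine is part of the chemistry panel (Protocol 6.6.1). Chemistry is drawn at every on-treatment visit (Protocol Appendix 2), and height is measured at every study visit (Protocol 6.6.5).

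SAP 7.2.1 gives descriptive statistics for values and changes from baseline for eleven analytes: "ALT, AST, total bilirubin, alkaline phosphatase, hemoglobin, reticulocytes, white blood cell (WBC), neutrophils, lymphocytes, platelets, and INR as follows". Creatinine and eGFR are not among them. SAP 5.2 lists Schwartz eGFR as a baseline characteristic, and the SAP does not return to it.

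SAP 7.2.2.2 tabulates treatment-emergent graded abnormalities by analyte, so creatinine does appear there. Grades come from Protocol Appendix 3, where creatinine Grade 1 is "> 1.50 to 2.00 mg/dL" with no age band. Other rows, such as hemoglobin, phosphate and albumin, do have pediatric or age-specific limits. The footnote to the creatinine row notes only that an overlap with the "normal range for creatinine may result for Male subjects >70 yrs". Under SAP 7.2.2, "Grade 0 includes all values that do not meet the criteria for an abnormality of at least Grade 1", and SAP 7.2.2.1 requires a rise of at least one grade for an abnormality to be treatment-emergent.

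Protocol 4.3 excludes subjects with an estimated GFR below 90 mL/min/1.73 m², "as calculated by the Schwartz Formula".

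**The concern.** A single absolute creatinine cut-off means different things at different body sizes. In the Schwartz formula eGFR is proportional to height divided by creatinine, so a short child with adequate renal function has a low creatinine and must rise a long way to reach 1.50 mg/dL. If most of the clinically interesting range lies below the first grade, the graded table can be empty while renal function changes materially.

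Safety and tolerability are the primary objective of the Treatment Phase, and Protocol 9.5 relies on laboratory tests as part of that evaluation. Renal function also bears on exposure: the main circulating metabolite, GS-331007, is the one "which is eliminated renally by active tubular secretion and glomerular filtration" (Protocol 1.5), and its AUCtau is the primary PK endpoint. A clean creatinine table for about 50 children aged 3 to <12 could be read as evidence of stable renal function when it carries little information on that question.

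**Working it through.** The plan states no figure of its own on this point, so there is none to reproduce.

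**Inputs**
- Schwartz formula, eGFR = k × L / Scr, with L the height in cm and Scr the serum creatinine in mg/dL (Protocol 6.6.10). The constant "for children 3- <12 years old is 0.55". It is also 0.55 for females aged 12 or over, and 0.70 for males aged 12 or over.
- Lowest eGFR allowed at entry: 90 (Protocol 4.3).
- Highest ungraded creatinine: 1.50 mg/dL (Protocol Appendix 3).
- Heights: not in the documents. I assume 90, 100, 120 and 140 cm to span the younger group.

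**Step 1.** Creatinine at the entry limit: Scr = k × L / 90. At 100 cm this is 0.55 × 100 / 90 = 0.611 mg/dL.

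**Step 2.** eGFR at the highest ungraded creatinine: k × L / 1.50. At 100 cm this is 55 / 1.50 = 36.7.

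**Step 3.** Rise that stays Grade 0: 1.50 divided by the Step 1 value. At 100 cm this is 1.50 / 0.611 = 2.45-fold.

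| Height (k = 0.55) | Scr at eGFR 90 | eGFR at Scr 1.50 | Creatinine rise | Fall in eGFR from 90 |
|---|---|---|---|---|
| 90 cm | 0.550 | 33.0 | 2.7-fold | 63% |
| 100 cm | 0.611 | 36.7 | 2.5-fold | 59% |
| 120 cm | 0.733 | 44.0 | 2.0-fold | 51% |
| 140 cm | 0.856 | 51.3 | 1.8-fold | 43% |

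A child who enters with better function has further to fall ungraded: from eGFR 120 at 100 cm, the fall to 36.7 is 69%.

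**Step 4.** The same check in adolescents. A 160 cm female (k = 0.55) at 1.50 mg/dL has eGFR 0.55 × 160 / 1.50 = 58.7. A 170 cm male (k = 0.70) has 0.70 × 170 / 1.50 = 79.3, a fall of 12% from 90. The insensitivity is therefore mainly a feature of the younger children, is moderate in adolescent girls, and is minor in tall boys.

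**Step 5.** Other summaries that might fill the gap. The dedicated listing in SAP 7.2.2.2 covers Grade 3 or above, which for creatinine means above 3.00 mg/dL, or eGFR below 55 / 3.00 = 18.3 at 100 cm. Blood urea nitrogen has a grading row but is not in the chemistry panel of Protocol 6.6.1. Treatment Phase urinalysis is scheduled only at Screening and Day 1 (Protocol Appendix 2). None of these replaces a summary of creatinine change.

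**The case against.** Several points on the other side stand.

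- A reader might infer that creatinine is not summarized at all. That is wrong: SAP 7.2.2.2 tabulates it by grade. What is missing is a numeric or change-from-baseline summary.
- A reader might infer that a renal decline would go unseen. The documents do not support that either. SAP 7.2 lists every chemistry result by subject and flags values outside the reference range, even at Grade 0. Protocol 8.1.3 requires an adverse event record for laboratory abnormalities that need intervention or that lead to interruption, modification or discontinuation of study drug. Protocol 8.2.2 grades such events on clinical severity, so the 1.50 mg/dL limit does not constrain them. However, a listing gives no trend or incidence, eGFR is not derived after baseline, and Protocol 8.1.3 does not record abnormalities without clinical significance.
- It is tempting to call the scale an adult one. The creatinine row carries no age label, so that is inference. All that can be said is that it has no pediatric band.
- Renal elimination of GS-331007 is not evidence of renal toxicity. Protocol 1.5 describes this metabolite as inactive, and the documents report no renal signal. Exposure is also followed through sparse PK sampling and the population PK analysis.
- Protocol 9.5.4 commits only to summarizing a selection of laboratory data, so the SAP breaks no promise. The primary safety endpoint, adverse events leading to permanent discontinuation, does not depend on creatinine grades.
- Exclusion 6 (creatinine above 1.5 mg/dL) might look defective for the same reason. It is only redundant: the separate eGFR criterion still excludes anyone below 90.

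**Conclusion.** The point holds as a weakness in the choice of summaries, not as a departure from the protocol or a failure of safety monitoring. The one planned summary of on-treatment creatinine is blind up to 1.50 mg/dL. For children aged 3 to <12 at the entry limit, that allows an unreported fall in eGFR from 90 to between 33 and 51 over assumed heights of 90 to 140 cm.

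The result rests on the protocol's formula and entry limit, on the assumed heights, and on a child starting exactly at eGFR 90. Starting higher makes the ungraded fall larger; greater height, or k = 0.70, makes it smaller. It should not be extended to tall adolescent males, where the ungraded fall is about 12%.

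An absence of graded creatinine abnormalities in the younger group would be close to uninformative and should not be reported as evidence of stable renal function. Because the data exist and safety is the Treatment Phase primary objective, the change is worth making.

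**What to change.** - **SAP 7.2.1:** add creatinine and Schwartz eGFR (Protocol 6.6.10 formula, height from the same visit) by visit, with change from baseline, by treatment group and age group. State which age sets k. A boy who turns 12 on study would otherwise gain 0.70 / 0.55 = 1.27-fold in eGFR with no change in creatinine, so holding k at its baseline value is simplest.
- **SAP 7.2.2:** add the distribution of each subject's maximum on-treatment creatinine-to-baseline ratio, by age group.
- **If a count of on-treatment eGFR below 90 is shown:** restrict it to subjects at or above 90 at baseline, and show it with percent change from baseline. The limit of 90 is an entry criterion, not a safety threshold. At 100 cm, a move from 0.61 to 0.62 mg/dL takes eGFR from 55 / 0.61 = 90.2 to 55 / 0.62 = 88.7, a change of under 2% that a bare count would score as an event.
- **Graded table:** keep the Appendix 3 grades, with a footnote that the creatinine grades are insensitive in younger children.

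The cost is SAP wording and one or two tables. No new sample, visit or treatment rule is needed. The drawback is that some transient dips will be displayed. If the SAP is already final, SAP section 1 provides for documenting the change in the study report.
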